5.1 Study treatment

5.1.1 Investigational and control drugs

Table 5-1 Dosing scheme

Cohorts	Treatment Arm	KAE609 dose (mg)	Coartem dose (mg)	Dosing regimen	Available strengths to achieve recommended dose
1	1	10		QD 1 day	1 x 10 mg
	2		80/480	BID 3 days	80/480 mg or 4 x 20/120 mg
2	3	25		QD 1 day	1 x 25 mg
	4	10		QD 3 days	1 x 10 mg

	5		80/480	BID 3 days	80/480 mg or 4 x 20/120 mg
3	6	50		QD 1 day	1 x 50 mg
	7	25		QD 3 days	1 x 25 mg
	8		80/480	BID 3 days	80/480 mg or 4 x 20/120 mg
4	9	75		QD 1 day	1 x 25 mg 1 x 50 mg
	10	50		QD 3 days	1 x 50 mg
	11		80/480	BID 3 days	80/480 mg or 4 x 20/120 mg
5	12	150		QD 1 day	1 x 50 mg 1 x 50 mg 1 x 50 mg
	13		80/480	BID 3 days	80/480 mg
6	14	225		QD 1 day	1 x 50 mg 1 x 50 mg 1 x 50 mg 1 x 50 mg 1 x 25 mg
		110 (if required)		QD 1 day	1 x 50 mg 1 x 50 mg 1 x 10 mg
	15		80/480	BID 3 days	80/480 mg

5.1.2 Additional treatment

Antipyretic will be allowed for symptomatic management of fever (see [Section 5.5.7](#)). No other additional treatment beyond investigational drug and control drug are included in this trial. The control drug, Coartem, will be also provided as rescue medication ([Section 5.5.6](#)).

5.2 Treatment arms

Patients will be randomized in a 1:1 ratio between KAE609 single dose and Coartem in Cohort 1. Patients will be randomized in a 1:1:1 ratio between KAE609 single and repeated doses and Coartem in Cohort 2. Patients will be randomized in a 2:2:1 ratio between KAE609 single dose and repeated dose and Coartem in Cohort 3 and Cohort 4. Patients will be randomized in a 2:1 ratio between KAE609 single dose and Coartem in Cohort 5 and Cohort 6.

5.3 Treatment assignment and randomization

Randomization to treatment groups will be performed sequentially, cohort by cohort with a pause between cohorts to allow safety review (see [Section 3.1](#) and [Section 8.4](#)). Randomization may be put on hold within a cohort if there are patients experiencing safety events (see [Table 3-1](#)).

Once a cohort is active for enrollment, clinical sites will be informed and Interactive Response Technology (IRT) will be activated to accept patients. At Visit 101, all eligible patients will be randomized via the IRT to one of the treatment arms. The investigator or his/her delegate will contact the IRT after confirming that the patient fulfills all the inclusion/exclusion criteria. The IRT will assign a randomization number to the patient, which will be used to link the patient to a treatment arm and will specify a unique medication number for the first package of study drug to be dispensed to the patient. The randomization number will not be communicated to the caller. The randomization per cohort may be extended after consultation with the sponsor to cover for some early study/treatment discontinuation, for e.g., patient who was randomized but not treated by study medication etc.

The randomization numbers will be generated using the following procedure to ensure that treatment assignment is unbiased and concealed from patients and investigator staff. A patient randomization list will be produced by the IRT provider using a validated system that automates the random assignment of patient numbers to randomization numbers. These randomization numbers are linked to the different treatment arms, which in turn are linked to medication numbers. A separate medication list will be produced by or under the responsibility of Novartis Drug Supply Management using a validated system that automates the random assignment of medication numbers to packs containing the investigational drug(s).

No stratified randomization will be used in all the cohorts for this study.

The randomization scheme for patients/subjects will be reviewed and approved by a member of the Randomization Group.

5.4 Treatment blinding

Treatment will not be blinded to patients, investigator staff, and persons performing the clinical assessments since KAE609 is dosed once daily for one day or 3 days while Coartem is dosed twice daily for 3 days. Since the primary and secondary objectives of the trial are mainly based on objective laboratory assessments, this should not bias the safety endpoint and the efficacy assessments. To reduce the selection bias to treatment groups, IRT will be used to randomize patients to treatment groups and randomization data are kept strictly confidential until formal interim safety review or final analysis. At the time of interim safety review or final analysis, the randomization data will be loaded into the statistical programming system for access to programmers, trial statisticians, and pharmacokineticists.

At the time of formal interim safety review, if needed, summaries of results by cohort and treatment arm, if necessary, will be prepared only for Novartis internal/external experts to make decision for progress to the next cohort. These reports will be performed by the study biostatistics team (or deputy Contract Research Organization (CRO)) and pharmacokineticist if necessary (see [Section 9.7](#)).

Since this is open-label study, unblinding is not needed in the case of patient emergencies (see [Section 5.6](#)).

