3.2 Rationale for study design

This will be a multicenter, open-label, randomized, sequential, dose escalation study in adults with uncomplicated *P. falciparum* malaria.

The objective of this dose escalation study design is to characterize hepatic safety aspects of single- and multiple ascending doses of KAE609 and determine the maximum tolerated dose of the investigational drug KAE609 in malaria patients.

Dose escalation sequential design of the study is the standard design for evaluating safety and tolerability of a new chemical entity in the early phase (Phase I and II) of clinical development. Single doses up to 75 mg and repeated dosing up to 30 mg (3 day QD) have been evaluated in patients without any significant hepatic tolerability issue with the exception of LFT elevations observed in human challenge study at 10 mg single dose and 75 mg single dose in proof of concept (PoC) extension study. Single as well as repeated doses will be evaluated in this study since knowledge about safety profile of both schedules is important to inform further development of the dosing strategy with the best benefit risk profile. Single dosing is a necessary step prior to repeat dosing and allows the detection and management of adverse events (AE) which may be more severe with repeated dosing. Hence, to characterize the safety profile of the entire dose range of KAE609, patients will be first dosed with a single dose of lowest strength i.e., 10 mg and be escalated in a stepwise manner.

Coartem will be used as reference group to help distinguish if the hepatic events and other adverse events observed in the study are exclusive to KAE609 or resulting from the disease (*P. falciparum* malaria) itself.

Coartem will be dosed in the fed state. Furthermore, KAE609 will be dosed (irrespective of fed state) as single dose or QD for 3 days whereas Coartem will be dosed as twice a day (BID) for 3 days. Considering the differences in food requirement and differential frequency of administration for both the drugs, achieving blinding for patients and investigators is not feasible. The risk of bias arising out of the open-label design is minimized due to the fact that objective endpoints have been chosen for the study.

The patient population will be described in more detail in the [Section 4](#) below

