6.5.5 Electrocardiogram (ECG)

ECGs should be taken in triplicate within 5 minutes (after 10 minutes rest in the supine position to ensure a stable heart rate according to the ECG investigator manual). The preferred sequence of cardiovascular data collection during study visits is ECG collection first, followed by vital signs, and blood sampling.

The Fridericia QT correction formula (QTcF) should be used for clinical decisions.

Triplicate 12 lead ECGs are to be collected with ECG machines supplied by the central laboratory. Initial manual readout will be done locally in order to detect significant safety findings and allow for immediate response if needed. Local readout will be used for inclusion/exclusion purposes as central readout is not available within 24 hours.

In the event that a clinically significant ECG abnormality is identified at the site (e.g., severe arrhythmia, conduction abnormality of QTcF > 500 ms) the SAE must be reported according to the procedure described in [Section 7.2](#). If the patient is hemodynamically compromised, the investigator or a medically qualified person must initiate appropriate safety procedures without delay (for example cardioversion).

If QTcF is > 500 ms or QTcF increases ≥ 60 ms from baseline occur at any time, the patient should be assessed at the site and appropriate safety procedures (e.g., electrolyte correction) initiated without delay, if required. In addition two additional ECGs should be collected at 2-min intervals and provided to the central ECG laboratory for confirmation.

Clinically significant abnormalities must be recorded on the relevant section of the medical history/Current medical conditions/AE eCRF page as appropriate.

For 3 day regimens, any post-dose average QTc ≥ 500 ms will result in patient discontinuation from the treatment if there is a planned subsequent treatment.

Assessments will be done as indicated in the study assessment schedule table. All ECGs will be assessed centrally by an independent and blinded (with age of patient identified) cardiologist.

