6.5.8 Definition of Treatment Failure

Early treatment failure (ETF)

ETF is defined within this protocol as:

1. Clinical decline or lack of improvement (per Investigator) at 24 hours after first dose of treatment.
2. Development of any clinical complications (described in the WHO definition of complicated/severe malaria (WHO Guidelines 2010)) in the presence of parasitaemia within 72 hours of the first dose of treatment
3. Parasitaemia > 75 000/ μ L at or after 12 hours post-dose
4. Parasitaemia \geq baseline with or without fever at 36 hours after first dose of treatment
5. Any parasitaemia based on microscopy with fever, 48 hours post-dose
6. Parasitaemia > 100/ μ L based on microscopy with or without fever, 72 hours post-dose

Late Clinical Failure (LCF)

Development of danger signs or severe malaria on any day between Study Day 5 and Day 29 in the presence of parasitaemia without previously meeting any of the criteria of ETF

Presence of parasitaemia and axillary temperature $\geq 37.5^{\circ}\text{C}$ on any day between Study Day 5 and Day 29 without previously meeting any of the criteria of ETF

Late Parasitological Failure (LPF)

Presence of parasitaemia on any day between Study Day 5 and Day 29 and axillary temperature $< 37.5^{\circ}\text{C}$ without previously meeting any of the criteria of ETF or LCF

Adequate Clinical and Parasitological Response (ACPR):

Absence of parasitaemia on Study Day 29 irrespective of axillary temperature, without previously meeting any of the criteria of ETF or Late Treatment Failure or LPF.

Note: The first day of treatment with study medication is defined as Study Day 1 while the day prior to the first day of treatment is defined as Day -1. Compared to [WHO \(2016\)](#) which defined Day 0 as the first day of treatment with study medication, days after treatment referred to in this protocol are 1 day greater. For example, Study Day 29 in this protocol corresponds to Day 28 by [WHO \(2016\)](#).

Signs/symptoms indicative of severe/complicated malaria

Danger signs:

1. not able to drink
2. vomiting $>$ twice within preceding 24 hours
3. one convulsion within preceding 24 hours
4. unconscious state
5. unable to sit or stand

Signs of severe malaria:

Severe falciparum malaria is defined as one or more of the following, occurring in the absence of an identified alternative cause and in the presence of *P. falciparum* asexual parasitaemia:

- Impaired consciousness (Glasgow coma score < 11 in adults)

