##### Early treatment failure (ETF)

Patients will be classified as ETF upon meeting any of the following criteria:

- Clinical decline or lack of improvement (per Investigator) at 24 hours after first dose of treatment.

- Development of any clinical complications (described in the WHO definition of complicated/severe malaria (WHO Guidelines 2010) in the presence of parasitaemia (based on microscopy) within 72 hours of the first dose of treatment
- Parasitaemia  $> 75\,000/\mu\text{L}$  based on microscopy at or after 12 hours post first dose
- Parasitaemia  $\geq$  baseline based on microscopy with or without fever at 36 hours after the first dose of treatment
- Any parasitaemia based on microscopy with fever, 48 hours post first dose
- Parasitaemia  $> 100/\mu\text{L}$  based on microscopy with or without fever, 72 hours post first dose

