### **PCR-corrected ACPR at Day X where X=15 and 29**

- A patient is considered as non-responder at Day X if the patient experiences an ETF, LCF, or LPF from Day 5 to Day 7.
- A patient is also considered as non-responder if the parasitaemia is not cleared by Day X unless the patient discontinues the study prior to Day X without ETF, LCF, or LPF, in which case the response is considered as missing,
- A patient is considered as non-responder at Day X if the patient has a parasite recrudescence from Day 8 to Day X
- A patient is considered as responder (corrected ACPR) at Day X if the patient is not classified as a non-responder by Day 7 and has a new infection from Day 8 to Day X based on PCR genotyping unless that the patient did not have parasites cleared prior to the new infection, in which case the patient is considered as non-responder.
- A patient is considered as responder at Day X if the patient is not classified as a non-responder at Day X and the patient has a malaria blood film showing absence of parasitaemia at Day X or later if Day X is missing.
- The response for a patient is considered as missing/undetermined if
  - The patient has parasitaemia present from Day 8 to Day X for which the PCR genotyping of recrudescence or new infection is not determined.
  - The patient is not classified as a non-responder at Day X and the malaria blood film result at Day X is missing and not followed by a subsequent negative result.

Note - The outcome of PCR-corrected ACPR and uncorrected ACPR at a given day is categorized as responder or non-responder to distinguish from failure used in early treatment failure, late clinical failure or late parasitological failure. With this notation, ACPR rate is the proportion of responders.

A patient with presence of parasitaemia at more than 7 days after the first dose is considered as non-responder for uncorrected ACPR. We reclassify such a patient as responder for PCR-corrected ACPR if presence of parasitaemia at more than 7 days after the first dose is due to new infection. Whether the presence of parasitaemia after 7 days is due to recrudescence or new infection is determined and provided by the central laboratory.

The above definitions of ACPRs are purely based on the malaria blood film and PCR results without consideration for taking concomitant anti-malaria drugs. In statistical analyses, some

responses may be overridden for patients who take concomitant anti-malaria drugs (see [Sections 2.5 and 2.7](#)).

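### An unblinded investigator judgement at 24 hours can by itself make an early treatment failure, so the Protocol 5.4 assurance on open-label bias is too broad for ETF and ACPR, and the SAP does not settle how such a failure counts in ACPR

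*Protocol*

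**What the plan says.** **Blinding.** Protocol 5.4: "Treatment will not be blinded to patients, investigator staff, and persons performing the clinical assessments". It then argues that, because the objectives "are mainly based on objective laboratory assessments, this should not bias the safety endpoint and the efficacy assessments". Protocol 3.2 makes a related statement: "The risk of bias arising out of the open-label design is minimized due to the fact that objective endpoints have been chosen for the study".

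**ETF.** Criterion 1 in Protocol 5.5.6 and 6.5.8, repeated in SAP 2.1.1.1, is: "Clinical decline or lack of improvement (per Investigator) at 24 hours after first dose of treatment". The SAP makes the list disjunctive: "Patients will be classified as ETF upon meeting any of the following criteria". Protocol 5.5.6 attaches stopping study treatment and starting rescue medication to ETF.

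**ACPR.** Protocol 6.5.8 and the general ACPR definition in SAP 2.1.1.1 both require that no ETF criterion was met earlier. Protocol 9.5.1.1 counts rescue for *P. falciparum* malaria as treatment failure, except where it treats a new infection.

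**How the SAP describes these outcomes.** SAP 2.1.1.1 opens by saying that every treatment failure definition rests on *P. falciparum* asexual counts. SAP 2.7.2.2 says that ETF is determined from uncorrected parasite counts. The note after the PCR-corrected rules says: "The above definitions of ACPRs are purely based on the malaria blood film and PCR results".

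**Masked reading.** Protocol 6.5.5: "All ECGs will be assessed centrally by an independent and blinded" cardiologist. Neither document has such a requirement for blood films. The Amendment 1 summary records that masking of microscopy technicians was dropped as unnecessary in an open-label study.

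**The concern.** The Protocol 5.4 argument depends on outcomes that do not involve judgement by someone who knows the arm. ETF criterion 1 is exactly such a judgement. It feeds ETF directly, ACPR through the definition and through rescue, and parasite and fever clearance times through censoring at rescue (Protocol 9.5.1.3, SAP 2.7.2.3). Protocol 8.5 provides no adjudication, and no planned analysis separates failures by judgement from failures by count.

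At stake is the descriptive picture of efficacy by dose. If the threshold for declaring no improvement differs between arms, that picture mixes drug effect with expectation, while the plan describes the endpoints as objective. The SAP also leaves open whether a 24-hour ETF counts in ACPR at all, so two programmers could produce different ACPR rates from the same data.

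**Working it through.** The documents give no figure for judgement-based ETF or for bias, so there is nothing to reproduce. The check sets the definitions side by side and then sizes the effect of one patient.

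**Step 1. Does criterion 1 use a count?** No. Criteria 3 to 6 name a parasite density or a positive film, and criterion 2 requires severe malaria signs with parasitaemia. Criterion 1 names only the investigator's opinion at 24 hours. The SAP statements that failure and ETF rest on counts (opening of 2.1.1.1; 2.7.2.2) do not describe it.

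**Step 2. Does a 24-hour ETF count against ACPR?** By SAP 2.1.1, the day of first dose is Day 1. So 24 hours is Day 2, 72 hours is Day 4, and Day 5 begins the late-failure period.

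| Text | Patient with ETF by criterion 1 only, rescued with Coartem, film-negative at Day 29 |
|---|---|
| Protocol 6.5.8; SAP 2.1.1.1 general ACPR definition | Not ACPR |
| Protocol 9.5.1.1 (rescue rule) | Failure |
| SAP 2.1.1.1, uncorrected ACPR at Day X: ETF, LCF or LPF counted from Day 5 to Day X | Read literally, Day 2 lies outside the window, so responder |
| SAP 2.1.1.1, PCR-corrected ACPR at Day X: Day 5 to Day 7 | Same |
| SAP 2.7.2.1, data handling | No rule for rescue |

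The Day 5 start may be meant for LCF and LPF only, but the sentence does not say so. SAP section 4 lists no change from the protocol analyses.

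**Step 3. Size of one reclassified patient.** KAE609 arms have n = 10 (Cohorts 1 and 2) or n = 20 (later cohorts), from Protocol 3.1. The shift per patient is 1/n: 1/10 = 10 points, 1/20 = 5 points.

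Exact Clopper-Pearson 95% limits, the plan's own method, are: lower = Beta quantile 0.025 (x, n − x + 1); upper = Beta quantile 0.975 (x + 1, n − x).

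| Criterion-1-only ETFs, no other ETF | n = 10 | n = 20 |
|---|---|---|
| 0 | 0% (0 to 30.8) | 0% (0 to 16.8) |
| 1 | 10% (0.3 to 44.5) | 5% (0.1 to 24.9) |
| 2 | 20% (2.5 to 55.6) | 10% (1.2 to 31.7) |

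For ACPR, on the reading that a 24-hour ETF counts, two such patients in an arm of 10 change 8/10 (44.4 to 97.5%) into 6/10 (26.2 to 87.8%).

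**Step 4. How likely is at least one?** The per-patient chance q is not in the documents, so it is assumed. P(at least one) = 1 − (1 − q)^n.

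| q (assumed) | n = 10 | n = 20 |
|---|---|---|
| 2% | 18% | 33% |
| 5% | 40% | 64% |
| 10% | 65% | 88% |

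Protocol 3.6 reports earlier ETFs (three patients, 42%, at 10 mg; one patient, 25%, at 20 mg) but not the criterion met, so it does not narrow q.

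**The case against.** Several points on the other side stand.

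- **The text is hedged.** A reader might infer that the protocol rules bias out. It does not. Protocol 5.4 qualifies its claim, and Protocol 3.2 speaks of risk being minimized and does not name efficacy.
- **Direction is not shown.** A reader might infer that the low-dose KAE609 arms are disadvantaged, because Protocol 3.1 and 3.6 expect the first two cohorts to be sub-therapeutic. But Protocol 3.6 also expects KAE609 to improve symptoms within the first 24 hours, which is criterion 1's time point. The criterion applies to Coartem patients too. Expectation could act either way.
- **The ACPR sentence has a narrower purpose.** "The above definitions of ACPRs are purely based on the malaria blood film and PCR results" continues by setting concomitant antimalarials aside, so it is loose wording more than a rule. The statements on counts elsewhere in the SAP have no such excuse.
- **Count-based measures are already planned.** The proportion with parasitaemia at 12, 24 and 48 hours does not use criterion 1, and the 12-hour value precedes any 24-hour judgement. Table 2-4 of the SAP plans an ETF listing, but does not say that it shows the criterion.
- **A simple re-derivation of ACPR would mislead.** After rescue at 24 hours, later counts in a KAE609 patient reflect Coartem. Dropping criterion 1 and reclassifying these patients as responders would credit Coartem's effect to KAE609.
- **Film reading.** Dropping technician masking was deliberate, and slide procedures sit in a laboratory manual that is not among the documents. Whether labels reveal the arm is unknown. The latest SAP update follows database lock, so relabelling cannot help films already read.

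None of this removes the central fact that an unblinded opinion alone defines an ETF, nor the conflict between the SAP's ACPR rules.

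**Conclusion.** The point holds in a limited form. Bias in ETF is possible through criterion 1. Bias in ACPR is possible on the reading in Protocol 6.5.8, Protocol 9.5.1.1 and the general SAP definition. Unmasked film reading adds a second route, through the other ETF criteria, parasite clearance time and ACPR. The shift is 10 points per patient at n = 10 and 5 points at n = 20. How often it would occur and in which direction cannot be determined from the documents, and the probabilities in Step 4 rest on an assumed q.

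The documents do not support saying that efficacy is biased against low doses, or that any planned inference changes. ETF and ACPR are secondary, descriptive and not tested against Coartem (Protocol 9.5, SAP 2.7). Neither the ALT/AST primary endpoint nor the escalation criteria use criterion 1. Severity is minor to moderate. The unreconciled ACPR rules need settling whatever one thinks about bias.

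**What to change.** 1. **Wording.** Limit the Protocol 5.4 claim to ALT/AST and other laboratory endpoints, naming criterion 1 and unmasked film reading as exceptions. Correct the SAP statements (opening of 2.1.1.1, the note after the PCR-corrected rules, and 2.7.2.2) that failure, ETF and ACPR rest only on counts, film or PCR.
2. **Reconcile the ACPR rules.** Bring the general ACPR definition and the rescue rule of Protocol 9.5.1.1 into line with the Day 5 wording in the SAP's Day X rules and with the data handling in SAP 2.7.2.1, so that the status of a 24-hour ETF is unambiguous.
3. **Reporting.** List the criterion met for every ETF, with the 24-hour parasite count against baseline. Report ETF as defined and again without criterion-1-only cases. For ACPR, keep rescued patients as non-responders and report how many are non-responders solely through criterion 1. Label any version that reclassifies them as an upper bound, because later counts reflect rescue Coartem.
4. **Films still to be read.** Label slides with subject number and time only, so that the existing reader does not see the arm.

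**Cost.** Some wording, one supportive table, extra listing columns and one labelling line, with no additional reader. The supportive ETF rate drops genuine clinical failures that met no other criterion. Because the 36- to 72-hour criteria are assessed after rescue in these patients, it should be read as a lower bound.
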